**EVALUATION CRITERIA:**

**Pharmacokinetic Assessments and Endpoints (PK Subset)**

**BID Dosing: Subjects weighing 120 kg or less:**

Blood samples for PK analysis of TPOXX in plasma will be collected on Day 1 before the first dose (0 hour) and at 2, 4, 6, 8, 10, 12 (before the second dose), 14, 16, 18, 20, 22, and 24 hours (before the first dose on Day 2); on Day 14 (before the first dose); and on Day 28 (before the first dose) and at 2, 4, 6, 8, 10, 12 (before the second dose on Day 28), 14, 16, 18, 20, 22, 24 (Day 29, AM), 48 (Day 30, AM), and 72 (Day 31, AM) hours after the first dose on Day 28.

**TID Dosing: Subjects weighing more than 120 kg:**

Blood samples for PK analysis of TPOXX in plasma will be collected on Day 1 before the first dose (0 hour) and at 2, 4, 6, 8 (before the second dose), 10, 12, 14, 16 (before the third dose), 18, 20, 22, and 24 hours (before the first dose on Day 2); on Day 14 (before the first dose); and on Day 28 (before the first dose) and at 2, 4, 6, 8 (before the second dose), 10, 12, 14, 16 (before the third dose), 18, 20, 22, 24 (Day 29, AM), 48 (Day 30, AM), and 72 (Day 31, AM) hours after the first dose on Day 28.

For PK blood samples, the acceptable window for collection from the scheduled collection time point will be as follows:  $\pm 15$  minutes from 0 to 24 hours (except where samples are collected predose) and  $\pm 60$  minutes from 48 to 72 hours.

The following plasma PK parameters will be calculated separately for BID and TID dosing as endpoints for TPOXX to the extent that data permit using actual sampling times rather than scheduled sampling times and will include, but are not limited to the following:

**Day 1:**

- Maximum observed plasma concentration ( $C_{max}$ ), reported separately for each dose
- Time to reach  $C_{max}$  ( $T_{max}$ ), reported separately for each dose
- Area under the plasma concentration-time curve (AUC) from time zero to 24 hours ( $AUC_{0-24}$ )
- AUC from time zero to tau where tau is the 8-hour or 12-hour dosing interval following the first dose ( $AUC_{tau}$ )

**Day 28:**

- $C_{max}$
- Average steady-state plasma concentration ( $C_{avg}$ )
- Trough plasma concentration ( $C_{trough}$ )
- Minimum observed plasma concentration ( $C_{min}$ )
- $T_{max}$
- $AUC_{0-24}$
- AUC from time zero to tau where tau is the 8-hour or 12-hour dosing interval ( $AUC_{tau}$ )
- AUC from time zero to the last measurable sample ( $AUC_{0-last}$ )

- AUC from time zero to infinity (AUC0-∞)
- Observed elimination rate constant ( $\lambda_z$ )
- Terminal elimination half-life (t1/2)
- Apparent clearance (CLss/F)
- Apparent volume of distribution (Vz/F)
- Accumulation ratio (Rac)
- %Fluctuation

**Safety Assessments:**

Safety and tolerability will be assessed by the following endpoints: monitoring and recording of AEs; clinical laboratory test results (hematology, serum chemistry, and urinalysis); pregnancy testing; vital sign measurements (systolic and diastolic blood pressures, heart rate, respiratory rate, and body temperature); 12-lead ECG results; and physical examination findings. A blood sample will be collected for all subjects who discontinue from the study for TPOXX plasma concentration *if the ET visit occurs within 30 hours after the subject's last dose of TPOXX/matching placebo* in order to collect information about the relationship between TPOXX blood level and ET from the study.

**STUDY DRUG, DOSAGE, AND ROUTE OF ADMINISTRATION:**

**Subjects Weighing 120 kg or Less:**

- An oral dose of 600 mg (3 × 200-mg capsules) TPOXX BID (every 12 hours [ $\pm 30$  minutes]) for 28 days
- An oral dose of placebo (3 capsules identical to TPOXX) BID (every 12 hours [ $\pm 30$  minutes]) for 28 days

**Subjects Weighing More Than 120 kg:**

- An oral dose of 600 mg (3 × 200-mg capsules) TPOXX TID (every 8 hours [ $\pm 30$  minutes]) for 28 days
- An oral dose of placebo (3 capsules identical to TPOXX) TID (every 8 hours [ $\pm 30$  minutes]) for 28 days

**STATISTICAL CONSIDERATIONS:**

A summary of statistical considerations is provided below. More specific descriptions of the statistical methods to be used will be described in the statistical analysis plan (SAP).

**Sample Size:**

There is no formal sample size calculation for this study. Although the sample size is not based on statistical power considerations, administration of TPOXX 600 mg to 300 subjects provides approximately 95% probability of observing at least 1 occurrence of any AE if the incidence of AEs in the study population is 1% and is considered adequate to provide a reasonable assessment of safety and tolerability. A sufficient number of subjects will be randomly assigned to ensure that at least 300 subjects receive at least 92% of the doses of the BID or TID dosing regimen of oral TPOXX 600 mg over the 28-day treatment period.

**Study Population:**

Adult subjects from 18 to 80 years old, inclusive, are eligible for this study. A total of at least 445 subjects will be enrolled and randomly assigned into stratified age groups (18 to 30 years, 31 to 45 years, 46 to 64 years, and 65 to 80 years). Approximately 356 subjects will be randomly assigned to receive active drug (TPOXX 600 mg) and 89 subjects will be randomly assigned to receive placebo. Overall, across all clinical investigative sites, a goal of approximately 20% of subjects (i.e., 89 subjects) or more will be enrolled and randomly assigned in each age group to ensure a representative investigation of the safety and PK across age groups.

**Analysis Populations:**

All populations will be identified and finalized before the database lock. All subjects who are randomly assigned are considered study subjects. Study populations are defined as the following:

- The Intent-to-Treat Population will include all subjects who were randomly assigned to the study (i.e., a randomization number and randomization date are present in the database).
- The Safety Population will include all subjects who received at least 1 dose of study drug (TPOXX or matching placebo).
- The Per-Protocol (PP) Safety Population will include all subjects who received at least 92% of the 600 mg BID or TID dosing regimen of TPOXX or matching placebo.
- The PK Population will include all subjects in the PK subset who have taken at least 92% of the 600 mg BID or TID dosing regimen of TPOXX, have sufficient drug concentrations in plasma, and have no protocol deviations or other circumstances that would exclude the subject from analysis.

**Pharmacokinetic Analyses:**

The PK Population will be used for the preparation of PK summaries and analyses.

Individual plasma concentration and time deviation data will be presented in a data listing. Plasma concentration data will be summarized by study day, time point, and study drug dosing regimen using the following descriptive statistics: number of subjects, arithmetic mean, SD, coefficient of variation (CV), minimum, median, and maximum. Individual and mean plasma concentration versus scheduled time profiles will be presented in figures on both linear and semilogarithmic scales. Mean concentration versus scheduled time profiles will be presented by the study drug dosing regimen.

The PK parameters of TPOXX will be analyzed using noncompartmental methods based on the actual sampling times. The individual PK parameters will be presented in data listings and summarized by study day and study drug dosing regimen using the following descriptive statistics: number of subjects, arithmetic mean, SD, CV, geometric mean, geometric SD, geometric CV, minimum, median, and maximum.

**Safety Analyses:**

The safety and tolerability data summaries will be presented separately for the Safety Population and the PP Safety Population and will also be presented by BID or TID study drug dosing regimen.

Adverse events will be coded by preferred term and system organ class using the latest version of the Medical Dictionary for Regulatory Activities. All AE data will be presented in a data listing. Treatment-emergent AEs will be summarized by treatment, BID and TID study drug dosing regimen, and overall, as well as by severity and relationship to study drug for the Safety Population and PP Safety Population. For any subject who discontinues the study for any reason, data will be summarized by treatment group, reason for discontinuation, if the drug concentration was collected, and the result of the bioanalysis. In addition, SAEs and AEs leading to subject study discontinuation will be presented in the data listings and summarized by treatment, dosing regimen, and overall.

The overall AE rate will be defined as the percentage of subjects in the Safety Population and PP Safety Population who report at least 1 postdose AE. The overall AE rate will be compared between treatment groups using Mantel-Haenszel test stratified for age group (18 to 30, 31 to 45, 46 to 64, and 65 to 80 years). If expected cell counts are less than 5, then Fisher's exact test will be applied. An exact unadjusted 95% confidence interval (CI), calculated using the Clopper-Pearson method, will be presented for each treatment group. For the difference in overall AE rates between treatment groups, a continuity corrected exact 95% CI around the difference will be calculated. In addition, the Mantel-Haenszel adjusted odds ratio and 95% CIs from the stratified analysis will be presented. The relationship of treatment group, age, clinical investigative site, and their interactions on overall AE rate will also be investigated using a logistic regression model; CIs for the odds ratios associated with each factor in the model will be presented. Further details will be included in the SAP.

Time from the first dose to the first AE or to discontinuation from study for any reason will be analyzed using Kaplan-Meier quartile estimates along with 2-sided 95% CIs. Treatment groups will be compared using the log rank test stratified by age group and site. If a subject does not experience any AE or does not discontinue from study, the time to first AE or time to discontinuation will be censored at the date of study completion.

Toxicity grades for laboratory tests will be determined according to the Division of Acquired Immune Deficiency Syndrome (DAIDS) AE Grading Table. The maximum postbaseline grade increase from baseline grade will be summarized by treatment group and BID and TID study drug dosing regimen and overall for the Safety Population and PP Safety Population using frequency and percentage of subjects with increase to grade 1, 2, 3, 4, 1 to 4, 2 to 4, and 3 to 4, respectively.

Actual values and changes from baseline for clinical laboratory test results, vital sign measurements, and 12-lead ECG results will be summarized by treatment group and BID and TID study drug dosing regimen at each time point using descriptive statistics (number of subjects, mean, SD, minimum, median, and maximum). Shift tables will be generated for clinical laboratory test results. Physical examination findings will be presented in a data listing.

Narratives will be presented for all deaths, subjects who reported SAEs, subjects withdrawn because of AEs, and grade 3 AEs deemed by the investigator to be possibly, probably, or definitely related to study drug.

**DATE OF PROTOCOL:** 01 August 2022

## **1. INTRODUCTION**

### **1.1 BACKGROUND**

Historically, variola virus, the etiologic agent of smallpox, has been one of the more important human pathogens. Smallpox is highly communicable and carries exceptionally high morbidity. Secondary attack rates from 30% to 80% have been reported among unvaccinated members of households. Smallpox is defined by 2 clinical forms, variola major and variola minor. Mortality rates range from 1% for variola minor to 30% for variola major. With the advent of biowarfare as an instrument of terrorism, smallpox can no longer be thought of as a disease only of historic impact.

In July 2018, the US Food and Drug Administration (FDA) approved oral TPOXX® for the treatment of human smallpox disease in adults and pediatric patients weighing at least 13 kilograms.

### **1.2 RATIONALE FOR STUDY**

Treatment with TPOXX following exposure to variola virus and prior to the onset of clinically diagnosed smallpox disease would constitute postexposure prophylaxis treatment. For human smallpox, the asymptomatic incubation period following exposure to the variola virus may range from 7 to 19 days (most commonly 12 to 14 days) postexposure. This approximately 2-week asymptomatic incubation period (with variability in duration) in humans before the development of secondary viremia, symptoms, and the generation of neutralizing antibody responses, necessitates the need for a longer treatment duration of TPOXX as a prophylactic. Humoral immune responses in the form of hemagglutination inhibition, complement fixing, and virus-neutralizing antibodies are detectable within approximately 5 days after the appearance of the rash and therefore approximately 12 to 24 days postexposure. To ensure the proper development of a neutralizing antibody response to the variola virus and to avoid a post-treatment virologic rebound, SIGA proposes the administration of TPOXX 600 mg for 28 days to support a postexposure prophylaxis treatment claim.

### **1.3 RATIONALE FOR DOSE SELECTION**

TPOXX 600 mg (3 × 200-mg capsules) two times a day (BID) is the approved dose of TPOXX for the treatment of smallpox in patients weighing between 13 kg and 120 kg, inclusive. The FDA and SIGA have agreed that TPOXX dosing for patients weighing 120 kg

or more should be adjusted to 600 mg TPOXX *three* times a day (TID). The 28-day TPOXX treatment duration, rather than the 14-day duration, was chosen for the postexposure prophylaxis indication as a longer treatment period may be necessary to provide protection from smallpox from the time of initial exposure to variola virus until the development of protective neutralizing antibodies. This accounts for the 7- to 17-day, asymptomatic stage; the subsequent 2- to 3-day, prodromal stage; and finally, the development of neutralizing antibodies, which are evident from about the sixth day following the onset of clinical symptoms and increase in antibody titer thereafter.

## **1.4 POTENTIAL RISKS AND BENEFITS**

### **1.4.1 Potential Risks**

The effect of TPOXX on a fetus or nursing baby is not yet known; therefore, women of childbearing potential participating in this study will be required to agree to use an acceptable means of birth control from signing of the informed consent form (ICF) and continuing through 30 days after the last dose of study drug. For all women of childbearing potential, serum pregnancy testing will be performed and checked by the investigator to confirm a negative test result at the screening visit. For women of childbearing potential in the pharmacokinetic (PK) subset, a urine pregnancy test will be performed at check-in on Day -1 and must be confirmed as negative by the investigator prior to randomization and before receipt of the first dose of study drug on Day 1. Additional serum pregnancy testing will be performed on Days 7, 13, 21, and on Day 29 dosing complete/early termination (ET) visit. For women of childbearing potential not in the PK subset, a urine pregnancy test will be performed at check-in on Day 1 and must be verified as negative by the investigator prior to randomization and before receipt of the first dose of study drug. Additional serum pregnancy testing will be performed on Days 7, 14, 21, and on Day 29 dosing complete/ET visit. Women who are pregnant or breastfeeding or plan to become pregnant within 3 months after study drug administration will be excluded from the study; if a female subject becomes pregnant during study participation, study drug dosing will be discontinued, and the subject will be withdrawn from the study ([Section 6.2.1.8](#)).

As with all drugs, there is potential risk of an allergic reaction. At this time, there is no definitive information on the allergic activity of TPOXX. Headache and nausea have been the most common adverse events (AEs) in clinical studies completed to date. There may be other side effects of TPOXX that are not yet known. Full details can be found in the TPOXX full prescribing information.

### **1.4.2 Known Potential Benefits**

As this study will be conducted in subjects free from smallpox, no direct health benefits from taking the study drug are expected. Study subjects may benefit from receiving the laboratory testing, electrocardiograms (ECGs), and physical examinations. Others may benefit from knowledge gained in this study that may aid in the use of TPOXX for the treatment of smallpox.

## **2. STUDY OBJECTIVES**

### **2.1 PRIMARY OBJECTIVE**

The primary objective of this study is to determine the safety and tolerability of TPOXX when administered orally for 28 days in adult subjects.

### **2.2 SECONDARY OBJECTIVE**

The secondary objective of this study is to describe the PK profile of TPOXX when administered orally for 28 days in adult subjects.

## **3. STUDY DESIGN**

This is a Phase 3, multicenter, double-blind, randomized, placebo-controlled study to assess the safety, tolerability, and PK of oral TPOXX 600 mg when administered for 28 days in adult subjects.

A total of at least 445 subjects (includes a PK subset of 40 subjects), ages 18 to 80, inclusive, will be enrolled and randomly assigned within stratified age groups (18 to 30 years, 31 to 45 years, 46 to 64 years, and 65 to 80 years) to 1 of 2 treatment groups in an overall randomization of 4:1 (approximately 356 subjects will receive TPOXX and 89 subjects will receive TPOXX matching placebo). There will be 2 dosing regimens based on the subjects body weight: subjects with a body weight of 120 kg or less will be administered either TPOXX 600 mg or placebo BID, 12 hours apart ( $\pm$ 30 minutes); and subjects with a body weight of more than 120 kg will be administered TPOXX 600 mg or placebo TID, 8 hours apart ( $\pm$ 30 minutes). The enrollment goal for the study is to randomly assign a sufficient number of subjects to ensure that at least 300 subjects receive at least 92% of the oral TPOXX 600 mg BID or TID dosing regimen over the 28-day treatment period. Overall, across all clinical investigative sites, a goal of approximately 20% of subjects (i.e., 89 subjects) or more will be enrolled and randomly assigned in each age group to ensure a

representative investigation of TPOXX safety and PK across age groups. The treatment groups will be as follows:

- Treatment Group 1: An oral dose of 600 mg (3 × 200-mg capsules) TPOXX BID (every 12 hours [ $\pm$ 30 minutes]) for subjects with a body weight of 120 kg or less or TID (every 8 hours [ $\pm$ 30 minutes]) for subjects with a body weight more than 120 kg for 28 days (Day 1 to Day 28).
- Treatment Group 2: An oral dose of placebo (3 capsules identical to TPOXX) BID (every 12 hours [ $\pm$ 30 minutes]) for subjects with a body weight of 120 kg or less or TID (every 8 hours [ $\pm$ 30 minutes]) for subjects with a body weight more than 120 kg for 28 days (Day 1 to Day 28).

When study drug is administered at the clinical investigative site, all subjects will be provided a meal (consisting of approximately 600 calories and 25 g of fat). The meal should be consumed within 30 minutes and prior to the administration of study drug (TPOXX or matching placebo). Subjects should be administered study drug as soon as possible following completion of the meal but no more than 30 minutes should elapse between meal completion and administration of study drug. Subjects should take study drug with 8 oz. (240 mL) of water. Subjects will be instructed at the screening visit and prior to check-in to the clinical investigative site on either Day –1 or Day 1 that other than water, no beverages may be ingested within 3 hours before or 3 hours after study drug administration.

When study drug (TPOXX or matching placebo) is administered at home, subjects will be instructed to take it within 30 minutes after the completion of a meal consisting of approximately 600 calories and 25 g of fat and with 8 oz. (240 mL) of water. Other than water, no beverages may be ingested within 3 hours before or 3 hours after taking study drug excluding a beverage that is being consumed as a part of the required meal.

Clinical investigative sites will provide subjects with instructions and dietary information in order to help them meet the study requirement for eating meals with an appropriate caloric and fat content before study drug dosing.

Clinical investigative sites will provide subjects with a subject diary and instructions to record the time that they completed their last meal before taking study drug in the subject diary. Subjects will be instructed to record that they have met the required caloric and fat intake of eating a meal containing approximately 600 calories and 25 g of fat before each dose of study drug.

Clinical investigative sites will instruct subjects to record the time that they take study drug in their subject diary. Subjects will follow a dosing regimen of study drug appropriate for their weight for 28 days and will be instructed to take their study drug at the same time of the day each day.

Safety assessments will include clinical laboratory test results (hematology, serum chemistry, and urinalysis), monitoring of AEs including serious AEs (SAEs), vital sign measurements (systolic and diastolic blood pressures, heart rate, respiratory rate, and body temperature), ECG results, and physical examination findings.

All subjects will have a follow-up telephone call 14 and 30 days after the last dose of study drug (Day 42 [+2 days] and Day 58 [+2 days], respectively) to report any AEs and SAEs. All AEs, SAEs, and clinically significant laboratory abnormalities will be followed until resolution or until stability of the abnormality has been demonstrated as determined by the investigator and/or medical monitor.

The study will consist of a screening period (Day -28 to Day -2), 1 check-in, on-site visits (Day 7, Day 14, and Day 21), a dosing complete/ET visit (Day 29), and 2 follow-up telephone calls (Day 42 [+2 days] and Day 58 [+2 days]).

The total duration of the study for each subject, including screening, treatment, and follow-up telephone calls, will be approximately 86 days.

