## **6.2.1 Adverse Events**

Adverse events will be assessed from the time of the first dose of study drug until Day 42. Serious AEs will be collected up to Day 58. All AEs, SAEs, and clinically significant laboratory abnormalities should be followed until they are resolved or until stability of the abnormality has been demonstrated as determined by the investigator and/or the medical monitor.

The investigator is responsible for ensuring that all AEs and SAEs are recorded in the eCRF and reported to SIGA, regardless of their relationship to study drug or clinical significance. If there is any doubt as to whether a clinical observation is an AE, the event should be reported.

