### **6.2.1.3 Reporting Adverse Events**

All AEs reported, observed, or recorded in the subject diary from the first dose of study drug through the follow-up telephone call on Day 42 (+2 days) will be recorded on the AE page in the eCRF. Information to be collected includes drug treatment, type of event, date and time of onset, investigator-specified assessment of severity and relationship to study drug, date and time of resolution of the event, seriousness, any required treatment or evaluations, and outcome. Any AEs resulting from concurrent illnesses, reactions to concurrent illnesses, reactions to concurrent medications, or progression of disease states must also be reported. The Medical Dictionary of Regulatory Activities will be used to code all AEs. This requirement indicates that for some events, follow-up may be required after the subject has

completed study participation. These events will be reported by SIGA, as required, to the FDA.

Any medical condition that is present at the time that the subject is screened but does not deteriorate should not be reported as an AE. However, if it deteriorates at any time during the study following the administration of study drug on Day 1, it should be recorded as an AE. Prior to this, medical conditions reported by subjects are considered medical history.

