#### **6.2.1.4 Reporting of Serious Adverse Events**

Any AE that is considered serious by the investigator or which meets SAE criteria ([Section 6.2.1.1](#)), or any other event or condition regardless of grade, which in their judgment represents a reportable event, must be reported to the medical monitor and SIGA as soon as the investigator becomes aware of the event. In addition, the event must be reported to PPD via the SAE hotline. The PPD SAE Report Form must be submitted within 24 hours of knowledge of the event. SIGA will be responsible for notifying the relevant regulatory authorities of any SAE as outlined in US Title 21 Code of Federal Regulations (CFR) Parts 312 and 320. The investigator is responsible for notifying the institutional review board (IRB) directly.

In addition, the investigator (or designee) must report any grade 3 (severe) AE that they deem possibly, probably, or definitely related to study drug to the medical monitor and SIGA within 24 hours after becoming aware of the event.

After notification from the investigator, SIGA will report all study drug-related and unexpected SAEs (those not listed in the TPOXX full prescribing information) to the FDA within 15 calendar days of first knowledge. Fatalities or life-threatening events assessed as related and unexpected will be reported to the FDA within 7 calendar days of first knowledge. The DSMB will also receive these reports (refer to [Section 9.3.3.1.4](#)).

For this study, the following contact information will be used for SAE reporting:

The collection and monitoring period for SAEs is 30 days after administration of the last dose of study drug. At the time of discharge or ET from the clinical study, the subject will be

instructed to notify the investigator of any SAEs that occur within 30 days after the last dose of study drug.

All subjects will have a follow-up telephone call 30 days after administration of the last dose of study drug (Day 58 [+2 days]) to report any SAEs.

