### **9.3. Adverse Events**

The primary objective of this study is to determine the safety and tolerability of TPOXX when administered orally for 28 days in adult subjects. The overall AE rate in the Safety Population and the Per-Protocol Safety Population will be compared between treatment groups using a stratified Mantel-Haenszel test accounting for age (18 to 30 years, 31 to 45 years, 46 to 64 years, and 65 to 80 years). If expected cell counts are less than 5, then Fisher's exact test will be applied. The AE rate is the number of subjects who report at least 1 post-dose AE expressed as a proportion of the number of subjects in the Safety Population and the Per-Protocol Safety Population. An exact unadjusted 95% confidence interval (CI), calculated using the Clopper-Pearson method, will be given for each treatment group. For the difference in AE rates between the treatment groups, a continually corrected exact 95% CI around the difference will be calculated. In addition, the Mantel-Haenszel adjusted odds ratio and 95% Cis from the stratified analysis will be presented.

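### For subjects who stop dosing before Day 28, the protocol gives two different ends to SAE collection and two dates for each follow-up call

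*Combined protocol and SAP*

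**What the plan says.** Dosing is planned "for 28 days (Day 1 to Day 28").

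**Call timing.** The synopsis and Section 3 state both anchors in one sentence: "All subjects will have a follow-up telephone call 14 and 30 days after the last dose of study drug (Day 42 [+2 days"), with the second call labelled Day 58 (+2). Section 6.2.1.4 does the same for the 30-day call. Section 4.3 has subjects agree to calls by study day only.

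**SAE collection.** Section 6.2.1: "Serious AEs will be collected up to Day 58". Note (s) of Table 9-1 and note (r) of Table 9-2 agree. Section 6.2.1.4: "The collection and monitoring period for SAEs is 30 days after administration of the last dose of study drug". That section also has the subject, at discharge or early termination, "instructed to notify the investigator of any SAEs that occur within 30 days after the last dose of study drug".

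**AE collection.** Section 6.2.1: "Adverse events will be assessed from the time of the first dose of study drug until Day 42". Section 6.2.1.3 records AEs "from the first dose of study drug through the follow-up telephone call on Day 42 (+2 days) will be recorded" in the eCRF. The schedule notes and SAP Section 9.3.3 use the same end point.

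**Early stoppers.** Section 4.4.2 asks for the ET assessments. It does not say whether the calls remain due afterwards, or from which date they are counted.

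**Analysis.** SAP Section 4.5.1 names the AE rate as the primary endpoint. SAP Section 9.3 defines it: "The AE rate is the number of subjects who report at least 1 post-dose AE expressed as a proportion" of the analysis population. There is no adjustment for length of follow-up.

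**The concern.** The plan treats 14 and 30 days after the last dose as the same dates as Day 42 and Day 58. That is true for completers and false for anyone who stops early. No section says which rule then governs.

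For SAEs this is a direct conflict between two collection periods. The last-dose version is also the one given to subjects at early termination, exactly the group for whom the two differ. Two sites could follow the protocol faithfully and collect SAEs over different periods.

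For AEs the stated collection period is not in conflict, but the call that elicits late AEs is. A non-PK subject has no listed contact after the ET visit except the two calls. If the first call is made at last dose + 14, scheduled AE questioning can end well before Day 42. A subject with no AE by then is still counted as AE-free, on a shorter window than a completer's. If early stopping differs between arms, the comparison of crude AE rates could be affected.

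**Working it through.** **1. The plan's own figures.** With the last dose on Day 28: 28 + 14 = 42 and 28 + 30 = 58. Adding the 28 days of screening, 28 + 58 = 86 days, the stated study duration. All three reproduce, but the first two only for a Day 28 last dose.

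**2. Last dose on Day d.** The last-dose anchor gives d + 14 and d + 30; the study-day anchor gives 42 and 58. The gap is 42 − (d + 14) = 58 − (d + 30) = 28 − d days.

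| Last dose | First call | SAE period ends | Gap | Gap as share of 58 days |
|---|---|---|---|---|
| Day 7 | Day 21 or 42 | Day 37 or 58 | 21 days | 36% |
| Day 14 | Day 28 or 42 | Day 44 or 58 | 14 days | 24% |
| Day 21 | Day 35 or 42 | Day 51 or 58 | 7 days | 12% |
| Day 28 | Day 42 | Day 58 | 0 | 0% |

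**3. Where the call window absorbs the gap.** With +2 days, a call at last dose + 14 can fall as late as d + 16. It reaches Day 42 when d ≥ 26. The same holds for the second call: d + 32 ≥ 58 when d ≥ 26. The readings separate for stops on Day 25 or earlier.

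**4. Which analysis population is exposed.** SAP Section 4.4 gives 56 doses (BID) or 84 (TID). The PP Safety threshold of 92% is 0.92 × 56 = 51.52, so 52 doses, and 0.92 × 84 = 77.28, so 78 doses. At two or three doses a day, 52/2 = 26 and 78/3 = 26: the threshold cannot be met before Day 26. By step 3 the mismatch beyond the call window therefore falls on subjects outside the PP Safety Population. They remain in the Safety Population.

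**5. Illustration for the AE rate.** The documents give no expected AE rate or dropout pattern, so this rests on assumptions. Take a constant AE hazard and a risk R by Day 42, so the hazard is h = −ln(1 − R)/42; for R = 40%, h = 0.01216 per day. A subject stops on Day d with no AE so far, and AE ascertainment ends at d + 14 instead of Day 42. The lost probability of being counted is

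exp(−14h) − exp(−(42 − d)h).

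For R = 40%:
- Day 7: 0.843 − 0.653 = 0.190
- Day 14: 0.843 − 0.711 = 0.132
- Day 21: 0.843 − 0.775 = 0.069

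For R from 20% to 60%, the ranges are 0.098 to 0.271 (Day 7), 0.067 to 0.194 (Day 14) and 0.034 to 0.104 (Day 21).

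**6. If the second call also elicits AEs.** Section 3 says both calls are for AEs and SAEs; Section 6.2.1.4 and the schedules treat the second as an SAE call. If AEs were also recorded at last dose + 30, the Day 7 loss at R = 40% falls to exp(−30h) − exp(−35h) = 0.694 − 0.653 = 0.041. For stops on Day 14 and Day 21 it is zero, because d + 30 is then Day 44 and Day 51, past Day 42.

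**The case against.** The strongest reply is that AE collection has one rule. Sections 6.2.1 and 6.2.1.3, the notes to both schedules, and SAP Section 9.3.3 all end it at Day 42 or the Day 42 call, and SAP Section 9.3.1 expects censoring there. Last dose + 14 appears only as call timing, and that call is labelled Day 42. This stands. A reader might infer that the protocol prescribes a much shorter AE window for early stoppers, or that the primary AE rate is biased by a known amount. The documents support neither. The effect arises only where a site times the first call from the last dose and then stops asking.

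Second, a 30-day post-dose SAE period may be what was intended, since the ET instruction says so. That may be true, but Section 6.2.1 and the schedules then say something else, so the conflict remains.

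Third, shorter depends on the yardstick. Under the last-dose reading every subject has 14 and 30 days after dosing; the study-day reading gives early stoppers more. It would be wrong to infer that early stoppers are under-followed after their last dose. The inequality is in time from first dose, the window that the crude proportion uses for completers.

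Fourth, time to first AE is analysed by Kaplan-Meier and a stratified log-rank test, which accommodate unequal follow-up, and the AE rate is also compared in the PP Safety Population. Both limit the damage. Neither repairs the crude Safety Population proportion.

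Follow-up of events to resolution does not answer the point: it concerns events already known, not detection of new ones.

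**Conclusion.** The conflict is real for SAE collection and for call timing in anyone whose last dose is before Day 28. Its size is exact: 28 − d days, for example 21 days (Day 37 against Day 58) after a Day 7 stop. Stops on Day 26 or 27 are covered by the call window.

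For the primary AE rate the risk is conditional and confined to the Safety Population. The 19, 13 and 7 percentage points for AE-free stops on Day 7, 14 and 21 rest on a constant hazard, a 40% risk by Day 42, and no AE ascertainment after the first call. They are losses per such subject, not a bias between arms. A between-arm effect needs early stopping that differs by arm, which the documents do not quantify; with similar stopping and similar AE risk the difference would move little. Subjects who stop because of an AE already count in the overall rate.

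This is worth correcting because it is cheap and affects safety capture in the subjects who stop early. It does not show that the primary comparison is invalid.

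**What to change.** Reconcile the synopsis and Sections 3, 4.4.2, 6.2.1 and 6.2.1.4 to one anchor for every dosed subject. The study-day anchor agrees with most of the current text and with the SAP: AEs to Day 42 (+2), SAEs to Day 58 (+2). Because no dose is planned after Day 28, it always covers 14 and 30 days after the last dose, and it gives the crude AE rate the same planned window for everyone.

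- In Section 4.4.2, state that both calls remain due after an ET visit unless the subject withdraws consent to contact.
- In Section 6.2.1.4, change the SAE period and the instruction given at early termination to match.
- In the SAP, align the censoring text. Section 9.3.1 gives two censoring dates for subjects without an AE: the last usable assessment and study completion. Section 9.3.2 places study completion at the Day 42 call although calls run to Day 58.

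The cost is a wording amendment needing IRB approval and an SAP revision. The number of calls is unchanged, but early stoppers are kept in contact longer (51 days after the last dose for a Day 7 stop: 58 − 7), with probably slightly more loss to contact.
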